9.1. Adverse Events

Adverse events will be coded using the MedDRA coding thesaurus (version 21.0). All AEs recorded in the clinical database starting after the last visit on the VMDN-003 study will be considered a treatment-emergent adverse event (TEAE). All AE summary tables will include the number and percentage of subjects with an AE within a category, system organ class (SOC), and preferred term.

An overall summary of the number and percentage of subjects with TEAEs will be provided by treatment group. Frequencies and percentages of the following will be included: subjects with any TEAE, subjects with any TEAE leading to discontinuation, subjects with any TEAE leading to death, and subjects with any serious treatment-emergent AE (SAE).

The incidence of TEAEs will be summarized with frequencies and percentages by the following:

- SOC and PT
- SOC and PT by maximum severity
- SOC and PT by relationship to study medication
- SOC and PT by relationship to injection procedure.
- SAEs by SOC and PT
- AEs of special interest by SOC and PT

There are 4 types of AEs of special interest (AESI):

- Ophthalmological events that could potentially suggest causality related to HGF and its angiogenic potential
- Acute cardiac events

- Foot ulcers
- AEs related to pregabalin or gabapentin and their occurrence rates with in conjunction with VM202

Adverse event data will be summarized by treatment group and by treatment group within baseline gabapentin and pregabalin use.

All adverse events will be presented in a listing.

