Incidence of Serious Treatment Emergent Adverse Events by System Organ Class and Preferred Term, and Gabapentin and/or Pregabalin use at Baseline Safety Population

Same shell as Table 14.3.1.2.1, update first line to say 'Subjects with at least one SAE'. Add 'SAE = Serious treatment emergent adverse event' to the abbreviation footnote. Add a row at the top of table reading "Group: Gabapentin and/or Pregabalin Use". Once all records from group are summarized, update row text to "Group: No Gabapentin and/or Pregabalin Use" and start table on a new page.

Table 14.3.3.1.1

Incidence of Serious Treatment Emergent Adverse Events of Special Interest by System Organ Class and Preferred Term Safety Population

Same shell as Table 14.3.1.2.1, update first line to say 'Subjects with at least one SAE'. Add 'SAE = Serious treatment emergent adverse event' to the abbreviation footnote.

Table 14.3.3.1.2

Incidence of Serious Treatment Emergent Adverse Events of Special Interest, by SOC, PT, and Gabapentin and/or Pregabalin use at Baseline Safety Population

Same shell as Table 14.3.1.2.1, update first line to say 'Subjects with at least one SAE'. Add 'SAE = Serious treatment emergent adverse event' to the abbreviation footnote. Add a row at the top of table reading "Group: Gabapentin and/or Pregabalin Use". Once all records from group are summarized, update row text to "Group: No Gabapentin and/or Pregabalin Use" and start table on a new page.

Helixmith Co., Ltd. Protocol VMDN-003b

CONFIDENTIAL

Page x of y <Version>

Table 14.3.6.1 Summary of Vital Signs Safety Population

Parameter: XXXXXXXXXX	X					
Study Visit Timepoint	Placebo (N=XX)		VM202 (N=XX)		Overall (N=XX)	
Statistic	Observed	CFB	Observed	CFB	Observed	CFB
Baseline [1]						
n	XX		XX		XX	
Mean (SD)	XX.X (XX.XX)		XX.X (XX.XX)		XX.X (XX.XX)	
Median	XX.X		XX.X		XX.X	
Q1, Q3	XX.X, XX.X		XX.X, XX.X		XX.X, XX.X	
Min, Max	XX, XX		XX, XX		XX, XX	
Day 365						
n	XX	XX	XX	XX	XX	XX
Mean (SD)	XX.X (XX.XX)	XX.X (XX.XX)	XX.X (XX.XX)	XX.X (XX.XX)	XX.X (XX.XX)	XX.X (XX.XX)
Median	XX.X	XX.X	XX.X	XX.X	XX.X	XX.X
Q1, Q3	XX.X, XX.X	XX.X, XX.X	XX.X, XX.X	XX.X, XX.X	XX.X, XX.X	XX.X, XX.X
Min, Max	XX, XX	XX, XX	XX, XX	XX, XX	XX, XX	XX, XX

Continue for all parameters include Sitting Systolic Blood Pressure (mmHg), Sitting Diastolic Blood Pressure (mmHg), Weight (kg), Heart Rate (beats/min), Respiration Rate (breaths/min), Temperature (C), Body Mass Index (kg/m2). Sort parameters based on CRF form order.

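### SAP 9.1 plans a summary of all treatment-emergent AEs of special interest, but both table shells for it count only serious ones

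*SAP*

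**What the plan says.** SAP 9.1 opens its list of incidence tables with "The incidence of TEAEs will be summarized with frequencies and percentages by the following". Six breakdowns follow. The last two are "SAEs by SOC and PT" and "AEs of special interest by SOC and PT", as separate items. The section then names four AESI types: ophthalmological events possibly linked to the angiogenic action of HGF, acute cardiac events, foot ulcers, and events related to pregabalin or gabapentin. None of the four is defined by seriousness.

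SAP 14.2 has two shells for AESIs:

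- Table 14.3.3.1.1: "Incidence of Serious Treatment Emergent Adverse Events of Special Interest by System Organ Class and Preferred Term Safety Population"
- Table 14.3.3.1.2: "Incidence of Serious Treatment Emergent Adverse Events of Special Interest, by SOC, PT, and Gabapentin and/or Pregabalin use at Baseline Safety Population"

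Both carry the programming instruction "Same shell as Table 14.3.1.2.1, update first line to say 'Subjects with at least one SAE", and both continue "Add 'SAE = Serious treatment emergent adverse event' to the abbreviation footnote". The entry for Table 14.3.3.1.1 in the SAP's table of contents has the same title as the shell.

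**The concern.** The text and the shells disagree on which events are counted. Under 9.1 an AESI enters the summary because of its type. Under the shells it must also be serious. A programmer normally builds from the shell, and here the title, first row and footnote all point to serious events only, so nothing within the shell would prompt a query.

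Evaluating long-term safety is the first study objective, and 9.1 singles out these four types for separate reporting. An eye event or foot ulcer that meets none of the seriousness criteria in Protocol 5.1 would be missing from the one table meant to bring such events together by treatment group. The fourth type refers expressly to occurrence rates, which a serious-only table cannot supply.

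**Working it through.** No arithmetic beyond counting is needed. The check sets 9.1 against the shells.

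**1. Breakdowns in SAP 9.1 against shells in SAP 14.2**

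| Breakdown in 9.1 | Shells | Same events counted? |
|---|---|---|
| SOC and PT | 14.3.1.2.1, 14.3.1.2.2 | Yes |
| Maximum severity | 14.3.1.3.1, 14.3.1.3.2 | Yes |
| Relationship to study medication | 14.3.1.4.1, 14.3.1.4.2 | Yes |
| Relationship to injection procedure | 14.3.1.5.1, 14.3.1.5.2 | Yes |
| SAEs | 14.3.2.1.1, 14.3.2.1.2 | Yes |
| AESIs | 14.3.3.1.1, 14.3.3.1.2 | No: serious only |

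Five of the six match; the AESI breakdown does not.

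**2. All AE table shells**

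- All TEAEs: the 8 tables in the first four rows above plus the two overview tables, 14.3.1.1.1 and 14.3.1.1.2: 8 + 2 = 10.
- All SAEs: 2.
- Serious AESIs: 2.
- Total: 10 + 2 + 2 = 14. Shells covering all AESIs: 0.

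**3. Whether another output fills the gap**

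- Overview Table 14.3.1.1.1 has six rows: any TEAE, related to study medication, related to injection procedure, leading to discontinuation, leading to death, and SAE. None counts AESIs.
- The shell for Listing 16.2.7.1 shows every AE but has no AESI flag, so the AESI count cannot be read from it without reclassifying events.
- The SOC/PT tables include non-serious AESIs but do not mark them as AESIs or total them.

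**4. What the shells deliver as written**

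The events counted in Table 14.3.3.1.1 are those that are both AESIs and SAEs. Every one is already in Table 14.3.2.1.1, so the AESI table is a subset of the SAE table. The same holds for 14.3.3.1.2 within 14.3.2.1.2. AESIs that are not serious are in neither pair.

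**5. Whether the SAP allows this to be corrected silently**

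SAP 13 lets titles, footnotes and the order of rows or columns change during programming without a SAP revision, as minor cosmetic matters. Going from serious AESIs to all AESIs changes which events are counted, and that is not cosmetic.

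**The case against.** The best case on the other side is that this is a copying slip with limited effect. The instructions under the two AESI shells repeat those of the SAE shells just above them, and SAP 14.2 holds other leftovers, such as references to Sections 6.5 and 8.4.2, which this SAP does not contain. Section 9.1 already states the intended content, so correcting the shells would carry out the plan without altering it. The events are still collected, tabulated among all TEAEs and listed. The protocol's AE and analysis sections do not mention AESIs, its analysis is descriptive, and no test or decision rests on this table.

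Much of this stands. Carry-over is the likeliest cause, the primary endpoint is still answered by the all-TEAE tables, and no data are lost. The lack of an AESI row in the overview table is not a fault in itself, since 9.1 does not ask for one there; it shows only that the count is not available elsewhere.

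It does not remove the conflict. The signed plan gives two different event sets for one output, and the more detailed instruction is the narrower one. A reader cannot exclude that serious-only was intended. The scope should not be left to be chosen once results by arm can be seen.

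**Conclusion.** The concern holds. Followed as written, the shells do not produce the AESI summary planned in SAP 9.1, and every non-serious AESI drops out of the grouped comparison of VM202 with placebo. Both AESI shells and the one AESI contents entry carry the restriction, and none of the 14 AE table shells covers all AESIs.

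This rests on reading the AESI item in 9.1 as unrestricted. The TEAE lead-in, the separate item for SAEs and the absence of a seriousness condition in the four types all support that reading. How many events would be left out cannot be estimated, because the documents give no AESI rates.

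It should be fixed, but it does not threaten the primary endpoint.

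**What to change.** In Tables 14.3.3.1.1 and 14.3.3.1.2 and the contents entry for the first:

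- delete the word Serious from the titles;
- change the first row of each shell to *Subjects with at least one treatment-emergent AESI*;
- amend the abbreviation footnote to match.

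Serious AESIs can be kept as a sub-row or a companion table. If a serious-only summary was intended, leave the shells and state the restriction in 9.1.

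The cost is two shells and one contents line, with no new data.

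Two inexpensive additions are worth considering, although their absence is not a contradiction in the SAP:

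- **Type rows.** Add one row per AESI type counting subjects with at least one such event. A type may span several SOCs, and the SOC rows then do not give its count.
- **Assignment rule.** Fix, before any unblinded analysis, how events are assigned to each type. Either version of the table needs a way to identify AESIs, and the documents do not set one out. It matters most for the gabapentin/pregabalin type. The tables by baseline use partly address use together with VM202, but Protocol 5.2 records relationship only to study medication, injection procedure and underlying disease.

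These additions cost four rows, one written rule and a short coding review before unblinding.

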14.3. Planned Listing Shells

Helixmith Co., Ltd. Protocol VMDN-003b

CONFIDENTIAL

Page x of y <Version>

Listing 16.2.1.1 Subject Disposition

T. S. Jack	Study	40.0-34		Completed Throu	igh Day 365?	Last Visit	Data Entry	Study Procedures	Taking gabapentin and/or pregabalin at time of
Subject ID	Center	Date of Exit	Yes/No	If No, Reason	If No, Explanation	Performed	Complete?	Completed	VMDN-003 Randomization?
xxxxx	XXXXXX	DDMMMYYYY	Yes				xx	Informed Consent Form; Vital Signs; AE/SAE Collection; Concomitant Medications; PGIC, Daily Pain and Sleep Interference Diary	Yes
XXXXX	xxxxx	DDMMMYYYY	Yes				xx	Informed Consent Form; Vital Signs; AE/SAE Collection; Concomitant Medications; PGIC, Daily Pain and Sleep Interference Diary	No
XXXXX	XXXXXX	DDMMMYYYY	No	XXXXXXX	XXXXXXXXXXX	XXXXXXXX X	XX	Informed Consent Form, AE/SAE Collection	No
xxxxx	xxxxxxx	DDMMMYYYY	Yes				XX	Informed Consent Form; Vital Signs; AE/SAE Collection; Concomitant Medications; PGIC, Daily Pain and Sleep Interference Diary	Yes
xxxxx	xxxxx	DDMMMYYYY	Yes				xx	Informed Consent Form; Vital Signs; AE/SAE Collection; Concomitant Medications; PGIC, Daily Pain and Sleep Interference Diary	No

CONFIDENTIAL

Page x of y <Version>

Listing 16.2.1.2.1 Inclusion and Exclusion Criteria

	Z	Date of:		Informed Consent	All Inclusion	Any Exclusion		
Subject ID	Screening	Informed Consent	HIPAA	Process [1]	Criteria Met? [2]	Criteria Met? [3]	Screen Failure?	
XXXXXX	DDMMMYYYY	DDMMMYYYY	DDMMMYYYY	1	Yes	No	No	
XXXXXX	DDMMMYYYY	DDMMMYYYY	DDMMMYYYY	1	No: 01, 02	No	Yes	
XXXXXX	DDMMMYYYY	DDMMMYYYY	DDMMMYYYY	3	No: 03	No	Yes	
XXXXXX	DDMMMYYYY	DDMMMYYYY	DDMMMYYYY	1	Yes	Yes: 01	Yes	
XXXXXX	DDMMMYYYY	DDMMMYYYY	DDMMMYYYY	2	Yes	Yes: 02	Yes	
XXXXXX	DDMMMYYYY	DDMMMYYYY	DDMMMYYYY	2	Yes	No	No	

^{[1] 1 =} The subject was informed of study requirements as described in the protocol; 2 = Informed consent was obtained prior to any study-related procedures; 3 = A copy of the signed and dated consent was given to subject.

Programming note: If more than 1 inclusion or exclusion criterion number exists, concatenate with a comma as shown above. Decode any relevant criteria in the footnotes as shown in the example. If no criteria are present for a column, remove the [2] and/or [3] from the column header.

^{[2] 01 =} subject randomized and dosed in the VMDN-003 study; 02 = Received Day 0, 14, 90, and 104 injections in VMDN-003 study; 03 = Currently in follow-up for the VMDN-003 study or having completed Day 270 within the last 90 days

^{[3] 01 =} Current use of an investigational drug or treatment; 02 = Unable or unwilling to give informed consent.

CONFIDENTIAL

Page x of y <Version>

Listing 16.2.1.2.2 Day 365 Visit Window

Subject ID	VMDN-003 Day 0 Visit Date	Target Day 365 Date	Day 365 Visit Window Start Date	Day 365 Visit Window End Date
xxxxxx	DDMMMYYYY	DDMMMYYYY	DDMMMYYYY	DDMMMYYYY
XXXXXX	DDMMMYYYY	DDMMMYYYY	DDMMMYYYY	DDMMMYYYY
XXXXXX	DDMMMYYYY	DDMMMYYYY	DDMMMYYYY	DDMMMYYYY
XXXXXX	DDMMMYYYY	DDMMMYYYY	DDMMMYYYY	DDMMMYYYY
XXXXXX	DDMMMYYYY	DDMMMYYYY	DDMMMYYYY	DDMMMYYYY
XXXXXX	DDMMMYYYY	DDMMMYYYY	DDMMMYYYY	DDMMMYYYY

CONFIDENTIAL

Page x of y <Version>

Listing 16.2.2 Protocol Deviations

VMDN-003 Treatment Received: XXXXXXXXX

Subject ID	Date of Visit (Visit)	Deviation; Specify	Category; Specify	Reported to the IRB?	Reason for Deviation
XXXXXX	DDMMMYYYY (XXXXXXX)	XXXXXXXXXXX; XXXXXXXXXXXXX	XXXXXX; XXXXXX	Y/N	XXXXXXX
		XXXXXXXXXXXXXXXXXXXXXXXXXXXXXXXXXXXXXX	XXXXXX; XXXXXX	Y/N	xxxxxxxxxxxx
XXXXXX	DDMMMYYYY (XXXXXXX)	XXXXXXXXXXX; XXXXXXXXXX	XXXXXX; XXXXXX	Y/N	xxxxxxxxxxxxxxx
		XXXXXXXXXXXXXXXXXXXXXXXXXXXXXXXXXXXXXX	XXXXXX; XXXXXX	Y/N	XXXXXXXXXX
XXXXXX	DDMMMYYYY (XXXXXXX)	XXXXXXXXXXXX; XXXXXXXXXXXX	XXXXXX; XXXXXX	Y/N	XXXXXXXXXXXXXXXXX

Programming note: If deviation affected eligibility, category will be inclusion or exclusion, and the criterion number will follow the semicolon.

CONFIDENTIAL

[figure not shown]
Page x of y <Version>

Listing 16.2.3 **Analysis Populations**

	Safety [1]	ITT [2]	mlTT [3]	Primary Reason(s) for Exclusion
xxxxxx	Yes	Yes	No	Day 365 visit not completed.
xxxxxx	Yes	Yes	Yes	
XXXXXX	Yes	Yes	No	Day 365 visit not completed.

^[1] The safety population includes all subjects that sign informed consent for the VMDN-003b study. [2] The ITT population includes all subjects that sign informed consent for the VMDN-003b study and who were randomized on the VMDN-003 study.

^[3] The mITT population includes all subjects that sign informed consent for the VMDN-003b study and who complete the day 365 visit.

CONFIDENTIAL

Page x of y <Version>

[figure not shown]
Listing 16.2.4 Demographics and Baseline Characteristics

VMDN-003 Treatment Received: XXXXXXXXX

Subject ID	Sex	Date of Birth	Age (years)	Ethnicity	Race	Height (cm)	BMI (kg/m2)
XXXXXX	XXXX	DDMMMYYY	xx	xxxxxx	XXXXXXX	xx	XX
XXXXXX	xxxxxx	DDMMMYYY	XX	XXXXXXX	XXXXXX	XX	XX
XXXXXX	XXXXXX	DDMMMYYY	xx	xxxxxx	XXXXXX	XX	XX
XXXXXX	xxxx	DDMMMYYY	XX	XXXXXXX	XXXXX	XX	XX
XXXXXX	XXXXXX	DDMMMYYY	xx	xxxxxx	XXXXXX	XX	xx
XXXXXX	XXXX	DDMMMYYY	XX	xxxxxx	xxxxxx	xx	XX

Note: Baseline values relative to the VMDN-003 baseline are listed.

Programming Note: If subject has multiple races, concatenate them. If subject has a race of 'Other', concatenate specify text with 'Other: '.

CONFIDENTIAL

Page x of y <Version>

Listing 16.2.6.1 Daily Pain and Sleep Interference Diary

[figure not shown]
VMDN-003 Treatment Received: XXXXXXXXX

Subject ID	Visit	Was Diary Completed?	Diary Date/Time (Study Day)	Pain Score	Sleep Interference Score	Mean Pain Score [1]	Mean Sleep Interference Score [1]
xxxxxx	XXXXXX	Yes/No	DDMMMYYYY:HH:MM (XX)	xx	XX		
, , , , , , , , , , , , , , , , , , , ,		Yes/No	DDMMMYYYY:HH:MM (XX)	XX	XX		
		Yes/No	DDMMMYYYY:HH:MM (XX)	XX	XX		
		Yes/No	DDMMMYYYY:HH:MM (XX)	XX	XX		
		Yes/No	DDMMMYYYY:HH:MM (XX)	XX	XX		
		Yes/No	DDMMMYYYY:HH:MM (XX)	XX	XX		
		Yes/No	DDMMMYYYY:HH:MM (XX)	XX	XX	XX	XX
XXXXXX	XXXXXX	Yes/No	DDMMMYYYY:HH:MM (XX)	XX	XX		
		Yes/No	DDMMMYYYY:HH:MM (XX)	XX	XX		
		Yes/No	DDMMMYYYY:HH:MM (XX)	XX	XX		
		Yes/No	DDMMMYYYY:HH:MM (XX)	XX	XX		
		Yes/No	DDMMMYYYY:HH:MM (XX)	XX	XX		
		Yes/No	DDMMMYYYY:HH:MM (XX)	XX	XX		
		Yes/No	DDMMMYYYY:HH:MM (XX)	XX	XX	XX	XX
XXXXXX	XXXXXX	Yes/No	DDMMMYYYY:HH:MM (XX)	XX	XX		
		Yes/No	DDMMMYYYY:HH:MM (XX)	XX	XX		
		Yes/No	DDMMMYYYY:HH:MM (XX)	XX	XX		
		Yes/No	DDMMMYYYY:HH:MM (XX)	XX	XX		
		Yes/No	DDMMMYYYY:HH:MM (XX)	XX	XX		
		Yes/No	DDMMMYYYY:HH:MM (XX)	XX	XX		
		Yes/No	DDMMMYYYY:HH:MM (XX)	XX	XX	XX	XX

Programming Note: Mean score will be printed on row for the last diary entry for each visit. Screening, Day 270, and Day 365 should be listed.

Note: Study day is calculated relative to the date of first study injection in the VMDN-003 study.

[1] The mean pain and scores are derived if at least 5 of 7 measurements prior to a visit are collected.

CONFIDENTIAL

[figure not shown]
Page x of y <Version>

Listing 16.2.6.2 Patient's Global Impression of Change (PGIC)

VMDN-003 Treatment Received: XXXXXXXXX

Subject ID	Visit	Was PGIC Completed?	Date of Assessment (Study Day)	Overall Status
XXXXXX	xxxxxx	Yes/No	DDMMMYYYY (XX)	xxxxxx
xxxxxx	XXXXXX	Yes/No	DDMMMYYYY (XX)	xxxxxx
xxxxxx	xxxxxx	Yes/No	DDMMMYYYY (XX)	xxxxxx

Note: Study day is calculated relative to the date of first study injection in the VMDN-003 study.

CONFIDENTIAL

Page x of y <Version>

[figure not shown]
Listing 16.2.7.1 Adverse Events

VMDN-003 Treatment Received: XXXXXXXXX

									Relationship to		
Subject ID	AE Numbe	Date of Onset (Study Day)/ End Date (Study er Day)	System Organ Class/ Preferred Term/ Verbatim Term	Worst Intensity/ Serious?/ Taken/Ad Frequency of Criteria Taken w		Action Taken/Action Taken with Study Drug	Study Medication	Injection Procedure	Underlying Disease		
xxxxx	XX	DDMMMYYYY (X)/ DDMMMYYYY (X)	XXXXXXXXXXXXXXXXXXXXXXXXXXXXXXXXXXXXXX	XXXXXX; XXXXX	XXXXXXXXX/ XXXXXXXXXX	XX	XX	XXXXXXXXXXXXXXXXXXXXXXXXXXXXXXXXXXXXXX		xxxxxxxx	XXXXXXXXX
XXXXX	XX	DDMMMYYYY (X)/ DDMMMYYYY (X)	XXXXXXXXXXXXXXXXXXXXXXXXXXXXXXXXXXXXXX	XXXXXX	XXXXXXXXX/ XXXXXXXXXX	XX	XX	XXXXXXXXXXXXXXXXXXXXXXXXXXXXXXXXXXXXXX		XXXXXXXX	XXXXXXXXX

Note: Study day is calculated relative to the date of first study injection in the VMDN-003 study. AEs were coded using MedDRA version 21.0.

Programming note: If Serious? is Yes, concatenate all serious criteria marked as Yes with a semicolon. If no events meet the criteria for display, present "No events are reported." SOC & PT text should be in proper case in table, as shown in the shell. If event is ongoing, display "ongoing" for End Date. If no comments are entered, do not display the row. If multiple outcomes exist, concatenate all outcomes with a semicolon.

Listing 16.2.7.2 Adverse Events Leading to Discontinuation of Study Drug

Same shell as 16.2.7.1, only include AEs with an action taken of discontinued study drug.

Listing 16.2.7.3
Adverse Events Leading to Death

Same shell as 16.2.7.1, only include AEs leading to death.

[figure not shown]
CONFIDENTIAL

Page x of y <Version>

Listing 16.2.9.1 Vital Signs

Subject ID	Visit	Date of Collection (Study Day)	Parameter	Units	Result
XXXXX	XXXXXX	DDMMMYYYY (XX)	Sitting Systolic Blood Pressure	mmHg	XX
			Sitting Diastolic Blood Pressure	mmHg	XX
			Weight	b/kg	XX
			Heart Rate	BEATS/MIN	XX
			Respiration Rate	BREATHS/MIN	XX
			Temperature	F/C	XX

Note: Study day is calculated relative to the date of first study injection in the VMDN-003 study.

CONFIDENTIAL

Page x of y <Version>

Listing 16.2.9.2 Prior and Concomitant Medications

VMDN-003 Treatment Received: XXXXXXXXX

Subject ID	ATC Class Level 3/ Preferred Base Name/ Trade Name of Medication	Indication	Taken for AE?	Start Date (Study Day)/ End Date (Study Day)	Dose/Unit	Route; Specify	Frequency	Ongoing?
xxxxxx	XXXXXXXXXXXXXXXXXXXXXXXXXXXXXXXXXXXXXX	XXXXXXX	XXX	DDMMMYYYY (X)/ DDMMMYYYY (X)	XXX	xxxxxx; xxxxxx	XXXXXXX	XX
	XXXXXXXXXXXXXXXXXXXXXXXXXXXXXXXXXXXXXX	xxxxxx	xxx	DDMMMYYYY (X)/ DDMMMYYYY (X)	XXX	xxxxxx	xxxxxx	xx
	XXXXXXXXXXXXXXXXXXXXXXXXXXXXXXXXXXXXXX	xxxxxx	xxx	DDMMMYYYY (X)/ DDMMMYYYY (X)	xxx	xxxxxx;xxxxxx	XXXXXX	XX

Abbreviation: ATC = anatomical therapeutic chemical; NA = Not applicable.

Note: Study day is calculated relative to the date of first study injection in the VMDN-003 study. Medications were coded using WHO-DDE March 2018 version.

Appendix 1:

Library of Abbreviations

Abbreviation	Definition
aCRF	annotated case report form
AD	associated documents
ADR	adverse drug reactions
AE	adverse event
AESI	adverse events special interest
ANCOVA	analysis of covariance
ATC	anatomical therapeutic chemical
BLQ	beneath limit of quantification
BMI	body mass index
BRD	business requirements document
BSL	biostatistician lead
CCGs	CRF completion guidelines
CD	compact disc
CDISC	clinical data interchange standards consortium
CEC	central ethics committee
CFR	code of federal regulations
CI	confidence intervals
CIOMS	council for international organizations of medical sciences
CIP	clinical investigational plan

Abbreviation	Definition
CM	clinical manager
CMP	clinical monitoring plan
COV	close out visit
CRA	clinical research associate
CRF	case report form
CRO	contract research organization
CS	clinically significant
CSM	clinical supply manager
CSR	clinical study report
CTA	clinical trial administrator
CTM	clinical trial manager
CTMS	clinical trial management system
DB	database
DBL	database lock
DBP	diastolic blood pressure
DCRF	data change request form
DDE	drug dispensing error form
DEA	drug enforcement administration
DIA	drug information association
DIS	data integration specification
DLT	dose limiting toxicity

Abbreviation	Definition	
DM	data management	
DMB	data monitoring board	
DMC	data monitoring committee	
DML	data management lead	
DMP	data management plan	
DNA	deoxyribonucleic acid	
DOB	date of birth	
DS	document specialist	
DSG	drug safety group	
DSM	drug supply management (drug distributor)	
DSMB	data safety monitoring board	
DSP	data safety plan	
DSUR	development safety update report	
DTS	data transfer specification	
DVD	digital video disk	
EC	ethics committee	
ECD	edit check and derivation specifications	
ECG	electrocardiogram	
eCRF	electronic case report form	
EDC	electronic data capture	
EMA	European medicines agency	

Abbreviation	Definition	
eTMF	electronic trial master file	
EU	European Union	
FA	full analysis	
FDA	food and drug administration	
FMP	file management plan	
FPFV	first patient first visit	
FPI	first patient in	
GCP	good clinical practice	
GMP	good manufacturing practices	
GPV	global pharmacovigilance	
HR	heart rate	
IB	investigator's brochure	
IC or ICF	informed consent or informed consent form	
ICH	international council for harmonization	
ID	identification	
IDM	independent drug monitoring	
IEC	independent ethics committee	
IM	investigator meeting	
IMV	interim monitoring visit	
IND	investigational new drug	
INDSR	investigational new drug safety reports	

Abbreviation	Definition	
IP	investigational product	
IRB	institutional review board	
IRF	inventory release file	
IRR	infusion related reactions	
IRT	interactive response technology	
ISF	investigator site file	
ITT	intent-to-treat	
IVRS	interactive voice response system	
IWRS	interactive web response system	
IxRS	interactive voice/web response system	
KPI	key performance indicator	
LAN	local area network	
LDM	lead data manager	
LMS	learning management system	
LLOQ	lower limit of quantification	
LPI	last patient in	
LPLV	last patient last visit	
LPO	last patient out	
MAAP	medical affairs and pharmacovigilance teams	
MAH	marketing authorization holder	
MedDRA	medical dictionary for regulatory activities	

Abbreviation	Definition
MHRA	medicines and healthcare products regulatory agency
MM	medical monitor
MMP	medical monitoring plan
MMRM	mixed effect model repeat measurement
MTD	maximum tolerated dose
MVR	monitoring visit report
N	number
NA	not applicable
NCS	non-clinically significant
NF	non-functional
PD	protocol deviation
PDGP	protocol deviation guidance plan
PE	physical examination
PGIC	Patients' Global Impression of Change
PI	principal investigator
PIN	personal identification number
PK	pharmacokinetic
PKAP	pharmacokinetic analysis plan
PM	project manager
PMP	project management plan
PP	per-protocol

Abbreviation	Definition
PS	project specialist
PV	pharmacovigilance
PVG	pharmacovigilance group
QA	quality assurance
QARC	quality assurance, risk and compliance
QC	quality control
QOL	quality of life
ROT	record of training
RR	respiratory rate or relative rate
RSM	regional site monitor
SAE	serious adverse event
SAP	statistical analysis plan
SAS®	a software system used for data analysis
SBP	systolic blood pressure
SC	study coordinator
SCR	software change request
SD	standard deviation
SDS	study design specifications
SDTM	study data tabulation model
SDV	source data verification

Abbreviation	Definition	
SECC	self-evident correction conventions	
SECP	self-evident correction plan	
SF	screen failure	
SFT or SFTP	secure file transfer or secure file transfer plan	
SIV	site initiation visit	
SLA	service level agreement	
SMP	safety management plan	
SOC	system organ class	
SOP	standard operating procedure	
sow	statement of work	
SQV	site qualification visit	
SUA	start-up associate	
SUSAR	suspected, unexpected, serious adverse (drug) reaction	
TA	trial assistant	
TEAE	treatment-emergent adverse event	
TMF	trial master file	
TOM	task ownership matrix	
UAT	user acceptance testing	
USA	United States of America	
UTC	universal coordinated time	
WAN	wide area network	

Abbreviation	Definition	
WAR	work at risk	
WG	working guideline	
WHO	world health organization	
WHO-DD	world health organization drug dictionary
